## 4. INVESTIGATIONAL PLAN

### 4.1. Overall Study Design and Plan

This is a phase 1, single center, randomized, double-blinded, placebo controlled, dose escalation clinical trial in which 135 healthy males and non-pregnant females ages 18-45 who met all eligibility criteria were to receive 3 doses of either dmLT vaccine or placebo, randomized in a 4:1 ratio. Cohort A and Cohort B participants received study product via oral administration. Cohort C and Cohort D participants received study product via sublingual administration. Cohort E participants received two of three planned doses of study product via intradermal administration prior to the study being terminated due to the COVID-19 pandemic. No participants were enrolled in planned Cohorts F, G, H, or I. Participants were screened by history, physical exam, and clinical laboratory tests, including a urine or serum pregnancy test for women of childbearing potential. A schematic of the planned study design is presented in [Table 1](#).

### 4.2. Discussion of Study Design, Including the Choice of Control Groups

This study was designed to assess the safety and immune responses of a range of doses of dmLT when administered by the oral, SL, or ID route; in participants residing in an endemic country for ETEC disease. Cohorts A and B received 3 vaccinations via the oral route at escalating doses. Cohorts C and D received 3 vaccinations via the sublingual route at escalating doses. Cohorts E received 2 vaccinations via the intradermal route. Three placebo recipients per cohort were included in the study in order to blind the participants and observer and not as a comparison group.

### 4.3. Selection of Study Population

The study population for DMID protocol 14-0031 is males and non-pregnant females, 18 to 45 years old, inclusive, who are in good health and meet all eligibility criteria. Potential participants were screened from the general population at the International Centre for Diarrheal Disease Research, Mirpur, Bangladesh.

#### Subject Inclusion Criteria

Study participants were eligible for this study if they fulfilled the inclusion criteria below:

1. Male or female age 18-45 years old, inclusive.
2. Provides written informed consent before initiation of any study procedures.
3. Healthy as judged by the site investigators and determined by medical history, medication history, and physical examination.
4. Capable of understanding, consenting, and complying with all the study visits and procedures.
5. Body Mass Index of no less than 18.5
6. Agrees not to participate in another clinical trial during the study period.
7. Agrees to complete all study visits and procedures.
8. Agrees not to donate blood to a blood bank for 12 months after receiving the last vaccine.

## Subject Exclusion Criteria

Participants were ineligible for any of the following conditions or reasons:

1. Women who are pregnant or lactating or have a positive urine pregnancy test at screening or on the day of vaccinations.  
*\*Note: all women presenting for screening will have urine pregnancy testing. "Females of childbearing potential must agree to use an efficacious hormonal or barrier method of birth control from screening and through 28 days post last dose of vaccine. Abstinence is also acceptable."*
2. Presence or history of a chronic medical condition\* that would, in the opinion of the investigator, render vaccination unsafe or interfere with the evaluation of the vaccine.  
*\* Note: this may include, but is not limited to: significant renal disease, unstable or progressive neurological disorders, diabetes, heart disease, asthma, lung disease, liver disease, organ transplant recipients and cancer.*
3. Presence of a significant dermatologic condition\*, or tattoo(s), scarring or significant skin damage at the vaccination site that would impede evaluation of local reactogenicity.  
*\* Note: this may include severe eczema, psoriasis or history of keloid formation. Participants with history of squamous cell or basal cell skin cancer that has been surgically excised and considered cured may be enrolled in the study if the skin cancer site is healed and is not at proposed vaccine administration site.*
4. Any developmental abnormality of the palate.
5. Participants diagnosed with autoimmune disorders, chronic inflammatory disorders or neurological disorders with a potential autoimmune correlation.
6. Use of long-term ( $\geq 2$  weeks) oral steroids, intranasal or topical prednisone (or equivalent), parenteral steroids, or high-dose inhaled steroids ( $> 800$   $\mu\text{g}/\text{day}$  of beclomethasone dipropionate or equivalent) within the preceding 6 months.
7. Has major psychiatric illness\* during last 12 months that in the investigator's opinion would preclude participation.  
*\* Note: Participants taking antipsychotic or antimanic drugs should not be enrolled. These include: aripiprazole, clozapine, ziprasidone, haloperidol, molindone, lamotrigine, gabapentin, topiramate, loxapine, thioridazine, thiothixene, pimozide, fluphenazine, risperidone, mesoridazine, quetiapine, trifluoperazine, chlorprothixene, chlorpromazine, perphenazine, olanzapine, carbamazepine, divalproex sodium, lithium carbonate, or lithium citrate. Participants taking a single antidepressant drug and are stable without decompensating symptoms in the preceding 3 months can be enrolled in the study.*
8. Use of prescription or over-the-counter (OTC) anti-inflammatory medications\* 48 hours prior to receiving the investigational product.  
*\* Note: This includes naproxen, aspirin, ibuprofen, and other non-steroidal anti-inflammatory drugs.*
9. Gastrointestinal symptoms\* in the past 24 hours or abdominal pain lasting for more than 2 weeks in the past 6 months.  
*\*Note: this may include, but is not limited to: abdominal pain or cramps, loss of appetite, nausea, general ill-feeling or vomiting.*
10. Moderate or severe diarrheal illness\* during the 6 weeks prior to enrollment.  
*\*Note: Moderate or severe diarrheal illness is defined by the passage of  $\geq 4$  unformed or loose stools (mix of liquid and solid components) in a 24-hour period*

11. History of chronic gastrointestinal illness\*.

*\*Note: this includes severe dyspepsia or gastroesophageal reflux disease, constipation, irritable bowel syndrome (IBS), hemorrhoids, diverticular disease, colitis, colon polyps, colon cancer, and inflammatory bowel disease. Mild or moderate heartburn or epigastric pain occurring no more than three times per week is permitted.*

12. Regular use (weekly or more often) of laxatives, anti-diarrheal, anti-constipation, or antacid therapy.

13. History of major gastrointestinal surgery, excluding uncomplicated appendectomy or cholecystectomy.

14. History of systemic antimicrobial treatment (i.e., topical treatments are not an exclusion) during the week prior to any administration of dmLT.

15. Acute febrile illness (body temperature  $\geq 38^{\circ}\text{C}$ ) during the week prior to enrollment.

16. Abnormal screening laboratories\*.

*\*Note: screening labs include white blood cell count (WBC), absolute neutrophil count (ANC), hemoglobin (Hg), platelet count, serum creatinine, serum albumin, alanine aminotransferase (ALT, also known as SGPT), and serologic testing for Hepatitis B virus surface antigen (HBsAg) and Hepatitis C virus (HCV) antibody.*

17. Isolation of specific bacteria\* from screening stool cultures.

*\*Note: bacteria include ETEC, Vibrio cholerae, and Shigella spp. Salmonella and Campylobacter will not be evaluated as part this criterion.*

18. Received an inactivated licensed vaccine within 2 weeks of enrollment or live licensed vaccine within 4 weeks of enrollment.

19. Received a cholera (licensed or experimental) vaccine, *E. coli* vaccine, or *Shigella* vaccine in the last 3 years.

20. History of receiving immune globulin or other blood product within the 3 months before enrollment in this study.

21. Currently enrolled in another study, involving an experimental agent. Participants involved in observational studies or surveys remain eligible.

22. Any condition that would, in the opinion of the Site Investigator, place the participant at an unacceptable risk of injury or render the participant unable to meet the requirements of the protocol.

23. Known allergies to study compound or components of the study vaccine.

24. Donating blood in the 8 weeks prior to study entry.

## 4.4. Treatments

### 4.4.1. Treatments Administered

Participants were to be administered three doses of dmLT vaccine or placebo. Cohort E participants were administered two of three planned doses.

### 4.4.2. Identity of Investigational Product(s)

LT(R192G/L211A), or dmLT, is a derivative of wild-type ETEC heat-labile enterotoxin that has been genetically modified by replacing the arginine at amino acid position 192 with glycine and the leucine at

amino acid position 211 with alanine. These two amino acid substitutions take place in proteolytic cleavage sites which are critical for activation of the secreted toxin molecules. The protein has been designated LT(R192G/L211A) and has been extensively evaluated in pre-clinical animal studies for its ability to induce anti-dmLT antibody responses, as well as its capacity to adjuvant the immune responses for co-administered antigens.

The dmLT vaccine was provided by PATH Vaccine Solutions. All Cohorts received lot number 001-08-16 manufactured at IDT Biologika Dessau. Placebo (0.9% Sodium Chloride Injection, United States Pharmacopeia) and sodium bicarbonate (NaHCO3) buffer (used in delivery of the orally administered dmLT) were provided by Fisher BioServices.

#### **4.4.3. Method of Assigning Subjects to Treatment Groups (Randomization)**

The randomization code was prepared by the Statistical and Data Coordinating Center (SDCC), Emmes. Enrollment/randomization were performed through the enrollment module in the electronic data capture system, maintained by the SDCC.

For each cohort, eligible participants were randomized and assigned in a 4:1 ratio to dmLT (n = 12) or placebo (n = 3) groups. The randomization was based on a variable blocked scheme to provide an approximately balanced allocation to the treatment groups during the study.

#### **4.4.4. Selection of Doses in the Study**

Oral dmLT administered alone in a dose of up to 100 µg and together with an inactivated ETEC vaccine and live attenuated ETEC vaccine in a dose of up to 25 µg have been found to be safe in Phase 1 studies. In DMID Protocol 09-0066 a single oral dose of dmLT in escalating doses of 5 µg, 25 µg, 50 µg, and 100 µg was found to be well tolerated and immunogenic, with immune responses plateauing at the 50-µg dose. [1] In DMID Protocol 12-0023 three sublingual doses of dmLT in escalating doses of 1 µg, 5 µg, 25 µg, and 50 µg were found to be well tolerated with 25 µg eliciting the most consistent immunogenic response. [4] In DMID Protocol 13-0013 (CSR pending) three intradermal doses of dmLT in escalating doses of 0.1 µg, 0.3 µg, 1.0 µg, and 2.0 µg dmLT were administered with no safety signals observed.

#### **4.4.5. Selection and Timing of Dose for Each Subject**

Cohort A and B participants received 3 doses administered orally in clinic on Day 1, Day 15, and Day 29. Cohort C and Cohort D received 3 doses administered sublingually in clinic on Day 1, Day 15, and Day 29. Cohort E participants received 2 doses administered intradermally in clinic on Day 1, Day 22.

#### **4.4.6. Blinding**

This is a double-blind study. While participants and study personnel were not blinded to cohort and route of administration, they were blinded to group assignment (i.e., placebo vs. vaccine) within a cohort. Study product was administered by an unblinded study product administrator, a study personnel licensed, registered, or certified to administer vaccines, who was not involved in study-related assessments and had no participant contact for data collection following study injection. Participants, investigators, and study personnel who performed any study-related assessments following study product administration, and laboratory personnel who performed immunologic assessments were blinded to the administration of vaccine or placebo, within each cohort. The randomization scheme was generated by the SDCC and provided only to the assigned unblinded study personnel (e.g., pharmacist who prepared study products and unblinded study product administrators). According to DMID policy, the study medical monitor (MM) responds to requests for

emergency unblinding, and instructs the SDCC to release treatment codes only if necessary to ensure that the participant receives appropriate clinical care. No emergency or other unplanned unblinding events occurred during the conduct of this study.

#### **4.4.7. Prior and Concomitant Therapy**

Participants were permitted to take birth control pills and vitamins throughout the course of the study; herbal supplements were not permitted. In addition, participants were instructed that prescription or OTC anti-inflammatory medications were not permitted in the 48 hours prior to receiving the investigational product. This included medications that contain naproxen, aspirin, ibuprofen, and other non-steroidal anti-inflammatory drugs. All concomitant medications (e.g., vitamins, antacids, analgesics, prescription medications) taken 28 days prior to vaccination were recorded in the concomitant medication data collection form. Any medications taken during the 7 days following a dose of vaccine were to be recorded on the participant's memory aid and/or reported to a research team member upon follow up clinic visit. All analgesics and prescription medications from 8 to 28 days post-vaccination were recorded in the concomitant medication data collection form.

If the investigator learned that a participant had taken a prohibited medication (see Section 4.3 inclusion/exclusion criteria) during the time immediately around the dosing of the investigational product, the investigator was to contact the DMID Clinical Project Manager and MO for instructions regarding the participant's continuation in the study.

#### **4.4.8. Treatment Compliance**

All participants received each dose of study product administered in the clinic. Participants were directly observed at the time of dosing by a member of the clinical research team who was licensed to administer vaccines.

### **4.5. Immunogenicity and Safety Variables**

See [Table 2](#) and [Table 3](#) for a schedule of study procedures.

#### **4.5.1. Safety Variables**

Safety, reactogenicity, and tolerability will be assessed by:

1. Frequency and Severity of Solicited Adverse Events – reactogenicity events occurring from vaccination through 7 days after each dose of vaccine is administered:
  - a) Local solicited events include: irritation of the oral cavity or tongue, diarrhea, nausea, vomiting, and abdominal discomfort for Oral Cohorts; irritation of the oral cavity or tongue, facial nerve disturbance, diarrhea, nausea, vomiting, or abdominal discomfort for Sublingual Cohorts; and injection site pain, redness, swelling, bruising, itching, hypo/hyper pigmentation and induration, vesicles or hardened mass for Intradermal Cohorts.
  - b) Systemic solicited events include: fever, feverishness, fatigue, malaise, myalgia, or headache for Oral and Sublingual Cohorts; and fever, feverishness, fatigue, malaise, myalgia, headache, diarrhea, nausea, vomiting, or abdominal discomfort for Intradermal Cohorts.
2. Frequency of participant withdrawals from first vaccination through the end of follow-up (Day 209 for Oral and Sublingual Cohorts, Day 223 for Intradermal Cohorts)
3. Frequency of discontinuation of study vaccination during the study

4. Frequency and severity of unsolicited vaccine-related non-serious adverse events (AE), including laboratory AE, from first vaccination through 28 days after the last dose of vaccine is administered (Day 57 for Oral and Sublingual Cohorts, Day 71 for Intradermal Cohorts)
5. Frequency of vaccine-related SAEs from the first vaccination through the end of follow-up (Day 209 for Oral and Sublingual Cohorts, Day 223 for Intradermal Cohorts)

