3.2 Study Outcome Measures

3.2.1 Primary Outcome Measures

The **Primary Safety Endpoints** to be used to evaluate reactogenicity, safety and tolerability are as follows:

- The occurrence of solicited local site and systemic reactogenicity events from vaccination through 7 days after each dose of vaccine is administered
- The occurrence of study withdrawals throughout the study
- The occurrence of discontinuation of study vaccination during the study

- The occurrence of unsolicited vaccine-related adverse events (AE), including laboratory AE, from first vaccination through 28 days after the last dose of vaccine is administered

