4 STUDY DESIGN

This is an outpatient Phase 1 double-blinded, placebo-controlled, dose-escalation trial in approximately 135 (plus any additional participants if needed to have minimal evaluable participants / cohort as described in [Table 1](#)) apparently healthy adult volunteers, age 18-45 years, who meet all the eligibility criteria and reside in Bangladesh, an endemic country for ETEC infection. The study population will be recruited from Mirpur, a densely populated urban slum community of Dhaka, Bangladesh, known as having a high rate of diarrheal, respiratory and enteric disease.

This clinical trial is designed to assess the safety, reactogenicity, tolerability, and immunogenicity of a range of dosages of dmLT administered by three different routes: oral, SL, or ID. The schematic of study design is presented in [Table 1](#). The oral and SL routes of administration will evaluate dosages of 5, 25, and 50 μ g of dmLT; the ID route of administration will evaluate dosages of 0.3, 1.0, and 2.0 μ g of dmLT. Participants will receive a total of three sequential doses of dmLT; the oral and SL routes will be at days 1, 15, and 29 and the ID route will be at days 1, 22, and 43. After each dose of study product, participants will be observed for 30-90 minutes, depending on the route of administration.

Safety, reactogenicity, and tolerability of the study products will be evaluated for each participant. Solicited local and systemic reactogenicity will be collected for 7 days after each vaccine administration. Memory Aids and digital thermometers will be given to participants to record solicited local and systemic reactogenicity including elevated body temperature (i.e., fever) at home, and they will be reviewed with the participants. Unsolicited AEs will be collected from the time of each study vaccination through 28 days after the last vaccination. Safety laboratories will be collected on Visit 7 or about 28 days after the last vaccination. Serious adverse events (SAEs) will be collected from the time of the first study vaccination through 6 months after the last study vaccination. Tolerability of the study products will be assessed by recording the occurrence of and reason for study withdrawals and discontinuation of study vaccination during the study.

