7.3.2 VISIT 3 - Second Vaccination (~14 days post dose 1 ±2 days)

- This visit is ~14 days after the first dose for oral and SL cohorts and ~21 days after the first dose for the ID cohorts (window ± 2 days)
- Confirm ongoing consent and review eligibility criteria with the participant prior to performing any study procedures, to include updating the medical history and concomitant medications
- Record oral temperature, pulse, and blood pressure
- Targeted physical examination, if indicated based on review of medical history
- Collect approximately 6 mL of venous blood:
 - 2 mL for serum ELISA and neutralization assays
 - 2 mL for ASC assay
 - 2 mL for ALS assay
- Collect stool (approximately 4 gm) and saliva (approximately 2 mL)
- 1-2 gm of stool frozen at $-80^{\circ}\text{C} \pm 15^{\circ}\text{C}$ for future use microbiome studies
- Urine pregnancy test for all women will be performed and must be negative prior to dosing. Provide instructions to women participants to avoid pregnancy through the 28 days from receipt of the last dose of vaccine.
- Perform pre-vaccination reactogenicity assessment
- Administer vaccine dose 2, per the randomization code and observing the required pre-vaccination fasting for oral and rinsing for SL dosing
- Provide memory aid and other 7-day solicited AE and reactogenicity instructions
- Ask participant if they still have the digital thermometer for recording daily oral temperature for seven days following administration of the study product and offer re-instruction on the use of the thermometer as needed.
- Perform post-vaccination reactogenicity assessment after 90 minutes for oral cohorts and after 30 minutes for SL and ID cohorts. This assessment is to include unsolicited AEs and SAEs.
- Provide stool sample collection container and instructions on how to collect stool sample
- Confirm date and time for Visit 4

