## 9.7. Vital Signs and Physical Evaluations

The baseline value will be defined as the last value obtained prior to the first vaccination/dose of study product. If a participant has repeated vital sign measurements on the same day, the value from the last evaluation will be used for analysis. Post-baseline, in the case of multiple observations (for example, from supplemental visits), the assessment value that is closest to the scheduled visit window will be used in the analyses. All the recorded data will be listed. If observations have the same distance to the scheduled assessment, the latest one will be used.

Vital sign measurements include systolic blood pressure, diastolic blood pressure, pulse, and oral temperature. Grading scales for vital signs are presented in [Table 9](#). Vital signs were assessed at Day 1, Day 8, Day 15, Day 22, Day 29, Day 36, Day 57, Day 114 and Day 209 for Oral and Sublingual Cohorts and at Day 1, Day 8, Day 22, and Day 29 for Intradermal Cohorts. Vital signs will be tabulated by severity, visit, and treatment group ([Table 160](#), [Table 161](#), [Table 162](#), [Table 163](#), and [Table 164](#); [Listing 25](#)).

Physical Examinations were performed at screening to assess general wellness. The following body systems were assessed: head, eyes, ears, nose, and throat; lymph nodes; skin; pulmonary; cardiovascular; abdominal; neurological; and musculoskeletal systems. At subsequent visits including enrollment a targeted physical examination was conducted if indicated based on review of medical history. Findings will be presented in Listing 26.

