**15. SUMMARY OF CHANGES IN THE CONDUCT OF THE STUDY OR PLANNED ANALYSES****Changes to Study Conduct**

- At the request of the local (icddr,b) DSMB, collection of serum bilirubin at screening and Visit 6 and collection of ALT and creatinine at Visit 6 were added to the safety labs. These results were not obtained for Cohorts A through C which were enrolled prior to the request.
- Due to a country-wide lockdown instituted in Bangladesh to combat the COVID-19 pandemic all Cohort E participants did not receive a third dose of study product. Cohort D participant Visits 8 and 9 and Cohort E participant Visits 6 through 9 were not conducted and no further cohorts were enrolled due to the pandemic.

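### SAP 4.5.1 item 4 ends the 28-day unsolicited-AE window for the intradermal cohort on Day 71, but Cohort E's last dose was on Day 22, so the window nominally ends on Day 50

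*SAP*

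**What the plan says.** The primary endpoint in Protocol 3.2.1 runs "from first vaccination through 28 days after the last dose of vaccine is administered", and SAP 3.2.1 repeats it. Neither gives a study day. SAP 4.5.1 item 4 keeps the dose-anchored rule and adds days in parentheses: "28 days after the last dose of vaccine is administered (Day 57 for Oral and Sublingual Cohorts, Day 71 for Intradermal Cohorts").

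The planned schedule in Protocol Section 4 is that "the oral and SL routes will be at days 1, 15, and 29 and the ID route will be at days 1, 22, and 43". For the intradermal route the SAP records something else. Section 4.4.5 states: "Cohort E participants received 2 doses administered intradermally in clinic on Day 1, Day 22". Section 15 adds that "all Cohort E participants did not receive a third dose of study product" and that "Cohort E participant Visits 6 through 9 were not conducted". SAP 4.1 confirms that no later intradermal cohort was enrolled, so Cohort E is the whole of that route.

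Two other places matter. The shell for SAP Table 91, which Table 92 follows, has one row for related unsolicited events within 28 days of the last dose and another running to 6 months; neither carries a study day. Protocol 9.1 item 3 equates the last dose with the third, an anchor that does not exist for Cohort E.

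**The concern.** Within one sentence of the SAP, the rule in words and the day in parentheses disagree for an entire route of administration, on a primary safety endpoint. The SAP was written after the study stopped, and other parts were adapted to that: Section 9.7 lists intradermal vital signs only at "Day 1, Day 8, Day 22, and Day 29 for Intradermal Cohorts", and the by-day solicited-event tables for Cohort E (Tables 131 to 134) cover two doses. Item 4 was not adapted.

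The SAP's definitions section (3.3) contains no derivation of the AE window, so 4.5.1 supplies the only study days a programmer has for building the flag that the windowed rows of Tables 91 and 92 need. A programmer who takes Day 71 would label events up to 49 days after the last dose as falling within 28 days of it. A reader of the report would also take Cohort E to have been followed for unsolicited events to Day 71, when the visits from Day 50 onward did not take place.

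**Working it through.** Formula: end of window = study day of last dose + 28.

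**Step 1: reproduce the SAP's figures.** With the planned third dose, oral/SL gives 29 + 28 = 57 and intradermal gives 43 + 28 = 71. Both match. The end-of-follow-up days in the same section match the same anchor: 29 + 180 = 209 and 43 + 180 = 223. The stated days therefore assume three doses, the third on its nominal day.

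**Step 2: use Cohort E's recorded last dose.** 22 + 28 = 50. Protocol 7.3.2 places dose 2 about "21 days after the first dose for the ID cohorts (window ± 2 days"), that is Day 20 to 24, so individual windows end between 20 + 28 = 48 and 24 + 28 = 52. Day 71 exceeds the nominal end by 71 − 50 = 21 days and lies 71 − 22 = 49 days after the last dose.

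**Step 3: the consequence for others, if Days 57 and 71 are applied as hard cut-offs.** Protocol 7.3.4 times oral/SL dose 3 at 14 ± 2 days after dose 2, and dose 2 is 14 ± 2 days after dose 1. Protocol Appendix A shows Day 29 ± 2.

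| Case | Last dose | True end | SAP day | SAP day minus true end |
|---|---|---|---|---|
| Oral/SL, dose 1 only | Day 1 | 29 | 57 | +28 |
| Oral/SL, doses 1 and 2 | Day 15 | 43 | 57 | +14 |
| Oral/SL, dose 3 at Day 29 ± 2 | Day 27 to 31 | 55 to 59 | 57 | +2 to −2 |
| Oral/SL, both ± 2 windows accumulate | Day 25 to 33 | 53 to 61 | 57 | +4 to −4 |
| Intradermal, dose 1 only | Day 1 | 29 | 71 | +42 |

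A positive figure means extra days counted; a negative one means days lost from the window.

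**Step 4: what was observed in Cohort E.** In the intradermal schedule (Protocol Appendix A, SAP Table 3) Visits 6 to 9 are Days 50, 71, 128 and 223. None was conducted. The visit that would have closed a 28-day window after dose 2 is therefore itself missing. The last intradermal day listed for vital signs is Day 29, which is 29 − 22 = 7 days after dose 2 and leaves 50 − 29 = 21 days of the window beyond it. Section 15 does not list Visit 5 (Day 43) as missed, but SAP 9.7 does not show it either. The SAP does not say whether events in that interval were ascertained in some other way.

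**The case against.** The best defence is that the SAP does not fix the window by study day at all. The operative rule is in words in the same sentence; the endpoint and the table row carry only those words; and nothing says the bracketed days override them. SAP 4.5.2 lists planned intradermal days that were never reached in the same way, as schedule labels. This defence stands for Cohorts A to D, where Day 57 is a fair nominal label for a three-dose completer. It does not rescue Day 71, which as a label is correct for nobody in the trial.

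Four stronger readings are tempting, and the documents do not support them.

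- *Events would be dropped.* SAP 9.3 includes every reported adverse event in the summaries, Listing 22 shows all unsolicited events, and Tables 91 and 92 have a second related-event row to 6 months. What could go wrong is assignment to the 28-day row.
- *Twenty-one extra days of events would be counted in Cohort E.* Protocol Section 4 and Section 7.6 tie collection of non-serious unsolicited events to 28 days after the last vaccination, and no scheduled visit took place from Day 50 onward. The 21 days measure a mislabelled window; no effect on event counts is shown.
- *Up to eight early stoppers exist in Cohorts A to D.* SAP Section 5 mentions 40 vaccinees with all three doses, against 4 × 12 = 48 planned. But SAP Table 4 presents 40 as evaluable vaccinees, a multiple of the minimum of 10 per cohort; evaluability also requires specimens; and SAP 4.4.5 says these cohorts received three doses. No early stopper is reported.
- *Item 5 makes the same error, and Day 223 should read Day 202 (22 + 180).* Item 5 is worded as running to the end of follow-up, so its days are planned final-visit days. The difficulty there is that those visits were not held.

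**Conclusion.** The Cohort E point holds on the SAP's own dosing record. Day 71 is wrong as the end of a window 28 days after the last dose; the nominal end is Day 50 (Day 48 to 52 for dose 2 within its window). The discrepancy is 21 days and covers the whole intradermal cohort, planned at 15 participants (12 dmLT, 3 placebo).

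For Cohorts A to D the point is conditional. Misdating of 2 to 4 days for in-window shifts in dose 3, or of 14 to 28 days for early stopping, arises only if Day 57 is programmed as a cut-off, and early stopping is not documented there.

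Correcting the number is necessary but not enough. Without a statement that the Cohort E visits from Day 50 were missed, a Day 50 window would still read as completed follow-up. This is a definitional error in a primary safety endpoint that is cheap to correct; the documents do not show that it changes any event count.

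**What to change.** - In SAP 4.5.1 item 4, define the window per participant as first dose through the date of the last dose actually received + 28 days. Put the derivation in SAP 3.3 and use that flag for the 28-day row of Tables 91 and 92.
- Label Days 57 and 71 as nominal for three-dose completers only, and give Day 50 as the nominal end for Cohort E.
- State beside it that Cohort E Visits 6 to 9 were not conducted, so scheduled follow-up over that window was incomplete, and describe the AE ascertainment actually achieved.
- Reconcile the wording of Protocol 9.1, which ties the window to the third dose, with the endpoint's anchor on the last dose administered.
- In item 5, report the SAE follow-up actually achieved. The planned final-visit day was not reached in Cohort E (Day 223) or in Cohort D (Day 209; Section 15 records its Visits 8 and 9 as not conducted). Do not simply replace Day 223 with Day 202.

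The cost is one derived date variable and a few sentences. No new data are needed.
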